6.2.2.2 Visit 2 – day 5±1

At visit 2 the following will be obtained and / or performed:

- ! Vital signs
- ! Adverse events
- ! Changes in concomitant therapy
- ! Administration of cytarabine (schedules A and C)
- ! Compliance check for and documentation of cytarabine administration on the scheduled previous days
- ! Safety lab as specified in the flow charts and section 5.2.5
- ! Pharmacokinetic blood samples according to Tables 10.1.2: 1 - 10.1.2: 2 (Appendix 10.1) (only schedules A and B). The date and time of blood sampling must be recorded in the eCRF.
- ! Disease assessment (clinical and in the blood)

After approval of Protocol Revision I, visit 2 is optional.

6.2.2.3 Visit 3 – day 10±2

At visit 3 the following will be obtained and / or performed:

- ! Vital signs
- ! Adverse events
- ! Changes in concomitant therapy
- ! Administration of cytarabine (schedules A and C)

- ! Compliance check for and documentation of cytarabine administration on the scheduled previous days (schedules A and C)
- ! Safety lab as specified in the flow charts and section 5.2.5
- ! Pharmacokinetic blood samples according to Tables 10.1.2: 1 - 10.1.2: 2 (Appendix 10.1) (only schedules A and B). The date and time of blood sampling must be recorded in the eCRF.
- ! Disease assessment (clinical and in the blood)
- ! After approval of Protocol Revision I, visit 2 is optional.

6.2.2.4 Visit 4 – day 15

6.2.2.4.1 Visit 4 – day 15 (for treatment schedules A and B)

At visit 4 the following will be obtained from and / or performed in patients allocated to treatment schedules A and B:

- ! Vital signs at time points specified in the flow charts
- ! Adverse events
- ! Changes in concomitant therapy
- ! Compliance check for and documentation of cytarabine administration on the scheduled previous days until day 10 (schedule A)
- ! ECG recording (digital, triplicate) at the following time points in treatment schedule A and B only (ECGs in cycle 1 are performed precisely at the related PK sampling time points)
 - prior to start of infusion of BI 6727 (every cycle)
 - immediately before the end of infusion of BI 6727 (every cycle)
 - 2 hours after the start of infusion (= 1 hour after end of BI 6727 infusion)
(1st treatment cycle only)
 - 4 -6 hours after the start of infusion (= 3-5 hours after end of BI 6727 infusion)
(1st treatment cycle only)
- ! Safety lab as specified in the flow charts and section 5.2.5
- ! Administration of the trial drug BI 6727
- ! Pharmacokinetic blood samples according to tables 1 (schedule A) and table 2 (schedule B) respectively in section 10.1.2 (Appendix 10.1) The date and time of blood sampling must be recorded in the eCRF.

- ! Disease assessment (clinical and in the blood)

6.2.2.4.2 Visit 4 – day 15±2 (for treatment schedule C)

At visit 4 the following will be obtained from and / or performed in patients allocated to treatment schedule C:

- ! Vital signs
- ! Adverse events
- ! Changes in concomitant therapy
- ! Compliance check for and documentation of cytarabine administration on the scheduled previous days until day 10
- ! Safety lab as specified in the flow charts and section 5.2.5
- ! Disease assessment (clinical and in the blood)

6.2.2.5 Visit 5 – day 19±2

At visit 5 the following will be obtained and / or performed:

- ! Vital signs
- ! Adverse events
- ! Changes in concomitant therapy
- ! Safety lab as specified in the flow charts and section 5.2.5
- ! Disease assessment (clinical and in the blood)
- ! After approval of Protocol Revision I, visit 2 is optional.

6.2.2.6 Visit 6 – day 23±2

At visit 6 the following will be obtained and / or performed:

- ! Vital signs
- ! Adverse events
- ! Changes in concomitant therapy
- ! Safety lab as specified in the flow charts and section 5.2.5

- ! Disease assessment (clinical and in the blood)
- ! After approval of Protocol Revision I, visit 2 is optional.

6.2.2.7 Visit 7 – day 28 + 3

A visit will be performed at the end of each treatment cycle, i.e. on day 28 (plus up to three days). This visit may coincide with day 1 of the following treatment cycle. A subsequent treatment cycle should not start earlier than day 29 of the 4-week cycle. Any delay of more than three weeks between the previous and the next treatment cycle should be discussed with the clinical monitor of BI.

If this visit coincides with day 1 of the following treatment cycle the examinations which are due at both visits need to be documented only in the eCRF pages of visit 7 and do not need to be replicated in the eCRF pages of visit 1.

- ! Physical examination including body weight and ECOG performance score
- ! Vital signs
- ! Adverse events
- ! Changes in concomitant therapy
- ! Safety lab as specified in the flow charts and section 5.2.5
- ! Serum pregnancy test for women of childbearing potential after every other cycle
- ! Pharmacokinetic blood samples according to Tables 10.1.2: 1 - 10.1.2: 2 (Appendix 10.1) (only schedules A and B). The date and time of blood sampling must be recorded in the eCRF.
- ! Disease assessment:
 - peripheral blood evaluation for leukaemia
 - bone marrow evaluation after the first treatment cycle for leukaemia and pharmacodynamics (FACS and cytospins see section 5.6), after first treatment cycle bone marrow evaluation according to 5.1.1. The bone marrow aspiration may be performed up to 3 days earlier depending on logistic requirements to allow for a timely continuation of therapy
 - clinical assessment of disease
 - if applicable imaging (or other appropriate means of assessment) of extramedullary manifestation of leukaemia
- ! Assessment of eligibility for a further treatment cycle

After approval of Protocol Revision I, physical examinations, weight, ECOG performance score, and safety laboratory examinations should be done as medically indicated at discretion of the investigator. The results are not required to be entered in the eCRF; documentation in the source data is sufficient. Only in case of findings that are qualifying as an (S)AE, the respective (S)AE will be reported (eCRF and SAE form, if applicable).

ECGs should be recorded prior to and at the end of volasertib infusions. No triplicate digital recording is required anymore. ECGs can be recorded with a local ECG machine.

Transmission for central analysis will be discontinued.

Bone marrow aspirations and disease assessments only have to be done per local standard of practice to support the decision on further treatment with volasertib. These efficacy data will not be entered in the eCRF; documentation in the source data is sufficient.

6.2.3 End of treatment and follow-up

6.2.3.1 Visit at the End of treatment

The end of treatment (EoT) information has to be obtained when the patient discontinues the treatment along with the information obtained at the visit scheduled for that time point. If the patient concludes the trial within a treatment cycle and not at the end of a treatment cycle, the information required to be collected at the end of a cycle shall be obtained also (please refer to [6.2.2.7](#)). Disease assessment needs to be done only if not yet performed within the past four weeks.

The following will be obtained and / or performed

- ! Resting 12-lead ECG (digital, triplicate)
- ! Physical examination, ECOG score, body weight
- ! Adverse events
- ! Outcome: in case the patient had PD the date of first diagnosis of PD has to be recorded
- ! Trial completion (including reason for conclusion or if applicable premature discontinuation of trial, date of last administration of the trial drug)

6.2.3.2 Follow-up visit

Follow-up visits will be performed after the EoT visit in case patients are not eligible for further treatment cycles until death, lost to follow-up or agreement between sponsor and coordinating investigator not to pursue further follow up visits. Follow-up visits should be performed at 12 weeks intervals or earlier if appropriate. Follow-up visits may also be performed by telephone interview in case the patient is unable to visit the investigator. The following will be obtained and / or performed.

- ! ECOG performance score

- ! AEs since last visit in case they occurred during the observational period (6 weeks after the last trial drug administration) or are considered drug-related (see [5.2.1](#) and [8.4.1](#))
- ! Follow-up of AEs in case they were not yet recovered at EoT
- ! Outcome: date death (if applicable), date of progression (in case, the patient experienced PD)
- ! Treatment with any other antileukaemia drug (report date of treatment and drug)

After approval of Protocol Revision I, Follow-up is completed 21 days after discontinuation of study drug.

6.2.3.3 End of the whole trial

The clinical trial will be analyzed and reported after all patients enrolled in the phase II part have either stopped treatment or have been treated for at least four months (i.e. are expected to have received at least four treatment cycles). The timepoint for the report is chosen, because no major changes in the readout of the primary endpoint of phase II (response rate) are expected after patients have received ≥ 4 cycles. If patients are still ongoing in the trial or phase I schedule B is not yet completed at the time of the report, the clinical trial database will be kept open to collect additional data that will be reported in a revised report. If patients are still ongoing on treatment ~ 2 years after randomization of the last patient in phase II a revised clinical trial report might be generated with the clinical trial database still kept open to collect additional data. The trial will be completed as soon as the last patient has completed his / her last visit. The final results will be reported in a revised report.

In case the trial is ended by the sponsor when patients are still being treated with a clinical benefit from BI 6727, the patients will be offered to be treated in a follow-up trial which will be set up and allow patients to receive therapy with BI 6727.

6.3 REMOVAL OF PATIENTS FROM THERAPY OR ASSESSMENT

A patient has to be withdrawn from the trial in case one of the following criteria applies:

- ! A patient withdraws consent (patients are free to discontinue their participation in this trial at any time without the need to justify this decision).
- ! A treatment cycle has been delayed for more than three weeks for other than medical reasons
- ! A patient is no longer able to participate in the trial (e.g. AEs unrelated to therapy or disease progression, surgery, concomitant diagnoses, concomitant therapies or administrative reasons). The investigator may also stop a patient's participation, if the patient is no longer able to attend trial visits.
- ! A patient is being administered forbidden concomitant medication (refer to [section 4.2.2](#))

A patient can be withdrawn after discussion between the sponsor and the investigator if eligibility criteria are violated and / or the patient fails to comply with the protocol.

All withdrawals will be documented and the reason for withdrawal recorded and discussed, as necessary, in the final report of the trial. As soon as a patient is withdrawn from the trial, the next scheduled visit and the EoT have to be performed if feasible. Every effort should be made to follow-up patients in case an AE is still ongoing at the time of withdrawal. Patients who withdraw after assignment / randomisation and prior to the first treatment will not be included in the analysis data set for efficacy evaluation. They will be entered into the trial database, the reason for withdrawal will be documented and reported descriptively as well as by patient listing in the final trial report.

A patient has to discontinue trial drug administration in case

- ! DLT occurs which does not recover to a degree that allows treatment continuation or a second episode of DLT occurs in this patient or
- ! PD develops, including deterioration of general condition due to disease progression

Patients included in the phase I part who have not completed at least one cycle will be replaced unless they discontinued the trial due to drug-related AEs.

Patients allocated to treatment schedules A or B in the phase I part of the trial who for administrative reasons omitted the second infusion in the first 4-week cycle and were unable to receive the missed infusion within the next two days will be replaced.

Patients allocated to treatment schedules A in the phase I part of the trial who for administrative reasons omitted more than two doses of cytarabine in the first 4-week cycle will be replaced.

None of the patients randomized in the phase II part of the trial will be replaced for any reason.

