- a on day one of the very first cycle only
- b ECGs are performed at time points specified in 5.2.7 and 6.2.2.1. In the first and second cycle ECGs are performed in triplicate at the related PK sampling time points. Furthermore triplicate ECGs are performed before and at the end of every subsequent BI 6727 infusion.
- c ECGs are performed at time points specified in 5.2.7 and 6.2.2.4. In the first and second cycle ECGs are performed in triplicate at the related PK sampling time points. Furthermore triplicate ECGs are performed before and at the end of every subsequent BI 6727 infusion.
- d optional, only after separate informed consent
- e pre-infusion, and at minutes 30 (≤ 5), 60 (≤ 10) and 120 (≤ 10) after start of BI 6727 infusion
- f before the first administration of the trial drug and after informed consent and review of in- and exclusion criteria
- g subcutaneous cytarabine is administered twice daily on day one until ten
- h including coagulation parameters (see section 5.2.5)
- i for women with childbearing potential at screening and after every other cycle
- k sampling at the time points as specified in table 1 in section 10.1.2. In cycle 2 only at -0.05 and 1 hour after dose.
- m within 14 days before first treatment. Cytogenetics and molecular genetics (see 5.3.4). Pharmacodynamic analysis, i.e. FACS and cytospins (see 5.6)
- n only in the first cycle on day 2, i.e. 24 hours after the end of the first BI 6727 administration: Pharmacodynamic analysis (see section 5.6)
- p initial response assessment after the first treatment cycle, this analysis may be performed up to 3 days earlier to allow for a timely continuation of the treatment. Pharmacodynamic analysis (FACS and cytospins, see section 5.6) at the end of the first cycle.
Bone marrow aspiration after repeated cycles according to 5.1.1. Additional bone marrow aspiration as necessary for confirmation of haematologic DLT (see section 5.2.3) or progressive disease.

FLOW CHART FOR TREATMENT SCHEDULE B
BI 6727 MONOTHERAPY (ONLY PHASE I PART OF THE TRIAL)

Trial Periods	Screen	Treatment							EoT	FU ^s
Cycle *		! 1								
Visit	Screen	1	2 ^t	3 ^t	4	5 ^t	6 ^t	7 ^{**}		
Days	-14 to -1	1 $\forall 1$	5 $\forall 2$	10 $\forall 2$	15 $\forall 2$	19 $\forall 2$	23 $\forall 2$	28 +3		
Informed consent	x									
Demographics	x									
Medical history	x									
Review of in-/exclusion criteria	x	x ^a								
Document ineligibility for intensive treatment	x									

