4.1.5 Blinding

This phase I / IIa trial will be performed according to an open design. Although a double-blind double-dummy design would be feasible, this would necessitate additional placebo-infusions/injections which are considered dispensable in this phase I/IIa exploratory trial in these highly compromised patients. Without placebo-infusions/injections, the obvious difference in treatment schedules precludes blinding of both the patient and the investigator. Therefore, no blinding is done. For similar technical reasons, the statistical analyses will be performed in an open fashion.

This open-label trial will also be handled in an open fashion by the sponsor throughout. The eCRF will contain information on randomised treatment.

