6.2.1 Screening and run-in phase

6.2.1.1 Screening Visit

The screening phase, i.e. the phase after informed consent and before the very first administration of the trial drug, may be as long as 14 days.

The following will be obtained and / or performed:

- ! Informed consent
- ! Demographics (sex, birth date, race)
- ! Medical history (oncological and relevant non-oncological)
- ! Review of inclusion and exclusion criteria (patient eligibility)
- ! Documentation of reasons why the patient is considered ineligible for intensive treatment
- ! Resting 12 lead-ECG (digital, triplicate)
- ! Blood sample for pharmacogenetic investigations (optional, only after signed separate informed consent)
- ! Physical examination, body height, weight, vital signs and ECOG performance score
- ! Concomitant therapy
- ! Safety laboratory, including coagulation parameters and urinalysis (see section 5.2.5)

- ! Serum pregnancy test for women of childbearing potential
- ! Disease assessment: peripheral blood and bone marrow evaluation for leukaemia, pharmacodynamics (FACS and cytospins see section 5.6), AML cytogenetics and molecular genetics (see section 5.3.4). Bone marrow aspiration performed before inclusion in the trial may be accepted as baseline assessment if done within fourteen days before first treatment administration
If applicable imaging (or other appropriate means of assessment) of extramedullary manifestation of leukaemia.
- ! Assignment / Randomisation

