7.3 PLANNED ANALYSES

Two analysis populations are defined for efficacy and safety analyses. For the phase I part the full analysis set (phase I) is defined, in analogy to the intention to treat population as the treated set with respect to phase I; i.e. all patients of phase I who have received at least one single dose of BI 6727 will be considered, including the patients who have been replaced for any reason (see section 6.3).

For the phase II part the full analysis set (phase II) is defined, in analogy to the intention to treat population as the treated set with respect to phase II; i.e. all patients of phase II who have received at least one single dose of either BI 6727 or cytarabine will be considered.

No per protocol population will be used for analyses. However protocol violations will be described.

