7.5 RANDOMISATION

In the phase I part of the trial patients will be assigned, not randomized, into escalating dosage groups by order of admission into the trial.

Randomisation will be performed in the phase IIa part of this trial. In phase IIa, equal numbers of patients will be randomised to the respective treatment schedules. The medical data service will provide randomisation envelopes that are generated using a validated system.

An eligible patient is reported by fax to the clinical monitor at Boehringer Ingelheim; in phase I the patient will be assigned to the treatment schedule (according to [4.1.2](#)), in the phase IIa part the clinical monitor will open the next randomisation envelope in the predetermined order. The result of the assignment / randomisation along with the appropriate starting dose (in phase I part) will be communicated to the investigator by the clinical monitor (for more information please refer to section [4.1.2](#) and the ISF).

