7. PLANNED ANALYSIS

For in-text tables, the set of summary statistics is: N (number of patients with non-missing values), mean, standard deviation (SD).

For end-of-text tables, the set of summary statistics is: N / Mean / SD / Min / Median / Max.

For appendix tables, the set of summary statistics is: N / Mean / SD / Min / Q1 (lower quartile) / Median / Q3 (upper quartile) / Max.

Tabulations of frequencies for categorical data will include all possible categories and will display the number of observations in a category as well as the percentage (%) relative to the respective treatment group. Percentages will be rounded to one decimal place. The category missing will be displayed if and only if there are actually missing values. Percentages will be based on all patients in the respective patient set whether they have non-missing values or not.

In general all analyses will be performed for the treated set (phase I) and the treated set (phase II) separately. No pooling across these two treated sets will be performed unless noted otherwise.

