7.4.1 Statistical Group Comparisons

All statistical group comparisons will be performed with respect to the treated set (phase II). The comparison of the treatment schedule to the control schedule will be based on the conditional power approach and on a stopping for futility check [[7,8.](#)]. The conditional power for showing superiority of a treatment schedule with respect to the control schedule at a later time point will be evaluated assuming that the final analysis is the interim analysis of a larger trial. These calculations will be based on an O'Brien-Fleming design with interim analysis to stop for futility. The assumptions are an information fraction of 60% of patients, an overall type I error of 5% (one-sided), 15% objective response rate in the control vs. 30% objective response rate in experimental arm and a power of 65% as described in the CTP. The

conditional power will be computed under the current trend hypothesis [8.] using the standardized logarithm of the odd's ratio of proportions as a test statistic (approximately $N(0,1)$ distributed). [REDACTED] will be used for these computations.

Additionally, similar computations will be performed for other scenarios with a planned sample size of approximately 86 patients at the assumed interim analysis (25% information fraction, alpha=0.025 and power 90%, 33% information fraction, alpha=0.025 and power 80% as well as 40% information fraction, alpha=0.05 and power 80%).

The conditional power will be evaluated in addition under the null hypothesis of no treatment effect and under the assumption that the true treatment effect (measured as the log odds ratio) captures only 50% of the observed treatment effect in order to check the robustness of the result.

Odds ratios, confidence intervals, and Fisher's exact test will be used to compare treatments in an exploratory manner if appropriate.

Additionally, objective response rates will be evaluated by a Bayesian approach with a non-informative prior (9.) given by a beta(1,1) distribution. Denoting the total number of patients per arm by n and the number of responders per arm by r this leads to a beta($1+r, 1+n-r$) distribution for the posterior (per arm separately).

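### Phase II response, EFS and OS are compared only in dosed patients, although the arm is known before the first dose; no all-randomised analysis is planned

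*Protocol*

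**What the plan says.** **Who is analysed.** Protocol 6.3: "Patients who withdraw after assignment / randomisation and prior to the first treatment will not be included in the analysis data set" for efficacy. These patients are entered in the database and reported with reasons, descriptively and by listing. Protocol 7.3 calls its phase II full analysis set analogous to intention to treat, but defines it by dosing: "all patients of phase II who have received at least one single dose of either BI 6727 or cytarabine will be considered". SAP 6.3 repeats this under the name treated set. SAP 7 makes it the default: "In general all analyses will be performed for the treated set (phase I) and the treated set (phase II) separately". Protocol 7.3.1.3 and SAP 7.4.1 put all group comparisons on it, and SAP 7.5 names no other set for EFS or OS.

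**When the arm becomes known.** Protocol 4.1.5: "This open-label trial will also be handled in an open fashion by the sponsor throughout". Flow chart note f places assignment or randomisation "before the first administration of the trial drug and after informed consent and review of in- and exclusion criteria". Under protocol 7.5 the monitor opens the envelope, and the result "will be communicated to the investigator by the clinical monitor". Protocol 6.2.1.1 lists randomisation among the screening procedures and says of screening: "the phase after informed consent and before the very first administration of the trial drug, may be as long as 14 days".

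**What the endpoints cover.** Protocol 5.1.2 and 5.1.5 define EFS and OS for everyone who entered the trial, timed from randomisation. SAP 6.7 sets day 1 as the day of randomisation. Having entered the trial is not defined. Protocol 6.3 also says that randomised phase II patients are not replaced.

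**The concern.** Patients, investigators and the sponsor can all know the arm before the first dose. A patient who then receives neither drug leaves the only randomised comparison, and the reason may depend on the arm. A combination patient who takes cytarabine but not BI 6727 stays in. The balance that randomisation gives is therefore not fully carried into the analysis, and the resulting bias can go in either direction.

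The plan also disagrees with itself in two places. The EFS and OS clock starts at randomisation, but a death between randomisation and first dose falls outside the analysed set. And a patient who withdraws after one dose without completing cycle 1 is indeterminate and counts as a non-responder (protocol 5.1.1.1), whereas one who withdraws just before that dose disappears from the denominator.

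At stake are the response comparison read against the 18.9% futility rule, which justifies the sample size in protocol 7.6.2, and the exploratory EFS and OS comparisons.

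**Working it through.** **Inputs from protocol 7.6.2:** response 15% (control) and 30% (combination), 43 patients per arm, critical one-sided p = 18.9%, stated power 78.3%. **From SAP 7.4.1:** the test statistic is the standardised log odds ratio.

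**Step 1: the plan's own figure.** With z(0.811) = 0.8816, z(0.783) = 0.7824 and mean rate 0.225:

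n per arm = [0.8816 × √(2 × 0.225 × 0.775) + 0.7824 × √(0.15 × 0.85 + 0.30 × 0.70)]² / 0.15² = (0.5206 + 0.4545)² / 0.0225 = 42.3, so 43.

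Power at 43 per arm, pooled variance: Φ(0.15 / √(0.34875/43) − 0.8816) = Φ(1.666 − 0.882) = 78.3%. The stated design reproduces. The 18.9% was taken as given.

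**Step 2: exact operating characteristics.** For a responders of n₁ (combination) and b of n₂ (control):

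z = ln[a(n₂ − b) / (b(n₁ − a))] / √[1/a + 1/(n₁ − a) + 1/b + 1/(n₂ − b)]

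with 0.5 added to all cells if one is zero. The result is a go if z is at least 0.8816. Binomial probabilities were summed over all outcomes. False-go uses 15% vs 15%; power uses 30% vs 15%. With nobody undosed, false-go is 0.1964 and power 0.7894. They differ slightly from the plan's figures because the data are discrete.

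The documents give no undosed count, so k = 1 or 2 in one arm is an assumption. Three cases:

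- (a) Treated set; undosed patients are non-responders: Bin(43, p) over 43 − k.
- (b) Treated set; losses unrelated to response: Bin(43 − k, p) over 43 − k.
- (c) All-randomised set; the same unrelated losses coded as failures: Bin(43 − k, p) over 43.

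| Arm losing patients | k | (a) false-go / power | (b) false-go / power | (c) false-go / power |
|---|---|---|---|---|
| Combination | 1 | 0.2111 / 0.7996 | 0.1979 / 0.7800 | 0.1842 / 0.7685 |
| Combination | 2 | 0.2256 / 0.8277 | 0.1975 / 0.7917 | 0.1724 / 0.7463 |
| Control | 1 | 0.1773 / 0.7799 | 0.1892 / 0.7931 | 0.2092 / 0.8023 |
| Control | 2 | 0.1592 / 0.7602 | 0.1815 / 0.7888 | 0.2225 / 0.8149 |

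Equal losses of non-responders in both arms leave 0.1964 / 0.7894 unchanged. Two unrelated losses in each arm give 0.1964 / 0.7749 under either set.

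**Step 3: how often the reading changes under (a).** One exclusion: 1.0% to 1.9% of trials. Two exclusions: 2.9% to 3.8%.

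**Step 4: examples.**

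- Borderline, 9 vs 6 responders of 43: z = ln(9 × 37 / (34 × 6)) / √(1/9 + 1/34 + 1/6 + 1/37) = 0.490 / 0.578 = 0.848, futile. With one undosed combination patient dropped (9/42): z = ln(9 × 37 / (33 × 6)) / √(1/9 + 1/33 + 1/6 + 1/37) = 0.520 / 0.579 = 0.898, a go.
- Clear, 13 vs 6 of 43: one-sided p = 0.037. Dropping four combination patients gives 0.021; dropping four controls gives 0.059.

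**The case against.** The strongest reply is about weight. Protocol 7.2 and SAP 3.3 declare everything exploratory. SAP 7.4.1 reads the 18.9% rule beside other conditional-power scenarios, Fisher's test and Bayesian probabilities. The undosed count may be zero. The wider range needs every undosed patient to be a non-responder and all losses to fall in one arm, and the 9 vs 6 example sits right at the cut-off. All of that stands and limits the severity.

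Second, coding undosed patients as failures is not free. If losses are unrelated to response, column (c) moves further from the no-loss values than column (b). That also stands, and it is the reason to keep the treated set as a sensitivity analysis. It does not justify having no all-randomised analysis, because the treated set rests on an assumption about why patients left that these data cannot confirm.

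Third, the 14 days run from consent to first dose, and no interval from randomisation to dosing is given; the next envelope is opened only after an eligible patient is reported. So the gap may be short, and selection before allocation is limited. Neither prevents withdrawal once the arm is known.

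Fourth, undosed patients who withdraw consent to contact add little to EFS or OS. True; the gain there is mainly early deaths and patients who remain contactable.

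Fifth, SAP 6.4, SAP section 9 and the interim analysis plan are not in the public text. SAP 6.4 is cited for genetic subgroups and missing ECOG scores, and SAP 7 and 7.4.1 are explicit about the set.

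**Conclusion.** The concern holds. Every phase II efficacy comparison is restricted to dosed patients, allocation is open before dosing, and the available text contains no all-randomised analysis. The EFS and OS definitions do not fit that set.

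The likely numerical effect is small: nil if nobody is undosed or if equal numbers of non-responders are lost, and at most about 4 percentage points in false-go or power for one or two non-responders lost from one arm. It matters for a borderline result. These sizes assume 43 randomised per arm, the SAP's log odds ratio statistic and the 18.9% cut-off. The change should be made, but its absence does not invalidate the trial.

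**What to change.** **Analysis sets (protocol 6.3 and 7.3; SAP 6.3, 7, 7.4.1 and 7.5).** Define a phase II randomised set, analysed by assigned arm, for response, EFS and OS. Define having entered the trial as randomised for phase II. Keep the treated set for safety and as a sensitivity analysis for response. Report the number undosed per arm, with reasons.

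**Response (SAP 5.1.2).** State that undosed patients are non-responders. The section already makes objective response negative unless best response is CR or CRi, and puts deaths before any assessment under PD. An explicit sentence helps because its assessment window begins at the start of treatment.

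**EFS and OS (protocol 6.2.3.2; SAP 5.2.1).** Clarify that survival follow-up covers undosed patients who still consent to contact. Protocol 6.3 already asks for an end-of-treatment visit where feasible, and protocol 7.4 calls for mortality follow-up. Deaths are already counted under SAP 5.2.1. For undosed living patients, replace censoring at 0 by censoring at the last date known to be event-free, where one exists.

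**Cost.** Mostly wording plus some survival follow-up, since undosed patients are already in the database; the 86 randomised patients are unchanged. The statistical cost is column (c) of the table: two control refusals raise false-go to about 22%, and two combination refusals lower power to 74.6%. The treated-set analysis alongside shows whether the reading depends on this coding.
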